### **5.1.1.2 Increased Incidence of Treatment-Emergent Resistance in Patients Less Than 5 Years of Age**

Xofluza is not indicated in patients less than 5 years of age due to increased incidence of treatment-emergent resistance in this age group. In clinical trials, the incidence of virus with treatment-emergent substitutions associated with reduced susceptibility to baloxavir (resistance) was higher in pediatric subjects younger than 5 years of age (43%, 36/83) **than in pediatric subjects  $\geq 5$  years** to <12 years of age (16%, 19/117) **or subjects  $\geq 12$  years of age (7%, 60/842)**. The potential for transmission of resistant strains in the community has not been determined.

Refer to the current USPI for XOFLUZA (baloxavir marboxil) for details.

### **5.1.1.3 Risk of Bacterial Infections**

There is no evidence of efficacy of Xofluza in any illness caused by pathogens other than influenza viruses. Serious bacterial infections may begin with influenza-like symptoms or may coexist with, or occur as, a complication of influenza. Xofluza has not been shown to prevent such complications.

Prescribers should be alert to potential secondary bacterial infections and treat them as appropriate.

Refer to the current USPI for XOFLUZA (baloxavir marboxil) for details.

## **5.1.2 Management of Patients Who Experience Adverse Events**

### **5.1.2.1 Dose Modifications**

No dose modification will be permitted during the study.

### **5.1.2.2 Treatment Interruption**

Treatment interruption is not allowed in this study. Study treatment should be discontinued in patients who meet the criteria listed in Section 4.1.2

## **5.2 SAFETY REPORTING OF ADVERSE EVENTS**

### **5.2.1 Specification of Safety Variables**

Safety assessments will consist of monitoring and reporting adverse events (AEs) and serious adverse events (SAEs) per protocol. This includes all events of death and any study-specific issue of concern.

### **5.2.2        Adverse Events**

An AE is any unfavorable and unintended sign, symptom, or disease temporally associated with the use of an investigational medicinal product (IMP) or other protocol-imposed intervention, regardless of attribution.

This includes the following:

- AEs not previously observed in the subject that emerge during the protocol-specified AE reporting period, including signs or symptoms associated with influenza that were not present prior to the AE reporting period.
- Complications that occur as a result of protocol-mandated interventions (e.g., invasive procedures such as cardiac catheterizations).
- If applicable, AEs that occur prior to assignment of study treatment associated with medication washout, no treatment run-in, or other protocol-mandated intervention.
- Preexisting medical conditions (other than the condition being studied) judged by the investigator to have worsened in severity or frequency or changed in character during the protocol-specified AE reporting period.

### **5.2.3        Serious Adverse Events**

An AE should be classified as an SAE if the following criteria are met:

- It results in death (i.e., the AE actually causes or leads to death).
- It is life threatening (i.e., the AE, in the view of the investigator, places the subject at immediate risk of death. It does not include an AE that, had it occurred in a more severe form, might have caused death).
- It requires or prolongs inpatient hospitalization.
- It results in persistent or significant disability/incapacity (i.e., the AE results in substantial disruption of the subject's ability to conduct normal life functions).
- It results in a congenital anomaly/birth defect in a neonate/infant born to a mother exposed to the IMP.
- It is considered a significant medical event by the investigator based on medical judgment (e.g., may jeopardize the subject or may require medical/surgical intervention to prevent one of the outcomes listed above).

## **5.3            METHODS AND TIMING FOR ASSESSING AND RECORDING SAFETY VARIABLES**

The investigator is responsible for ensuring that all AEs and SAEs that are observed or reported during the study are collected and reported to the FDA, appropriate IRB(s), and Genentech, Inc. in accordance with CFR 312.32 (IND Safety Reports).

### **5.3.1        Adverse Event Reporting Period**

The study period during which AEs and SAEs as described in Section 5.4.2.10 where the patient has been exposed to Genentech product must be reported - reporting period begins after informed consent is obtained and initiation of study treatment and ends 14 days following the last administration of study treatment or study discontinuation/termination, whichever is earlier. After this period, investigators should only report SAEs that are attributed to prior study treatment (Modify statement depending up on AESI Section 5.4.2.7.

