## **2. OBJECTIVES AND ENDPOINTS**

### **2.1 PRIMARY OBJECTIVE(S)**

This study seeks to demonstrate that the laboratory can mitigate respiratory virus transmission in underserved populations by using laboratory data to identify communities at risk for increase vial activity (hot spots) and intervening with a test-to-treat model provides increased access to influenza diagnostics and treatment in vulnerable and underserved communities.

1. The hot-spot frequency and hot spot score trend will be measured for each census tract to determine if the screen and treat intervention has an impact on reducing hot spot identification or hot spot score.
  - a. Following each mobile intervention, we will evaluate the hot spot score for the census tracts receiving a mobile screen and treat intervention and SVI-matched census tract not receiving an intervention for 14-days following the screen and treat intervention.
  - b. Patients will receive a follow-up phone call 14-days following their initial screening visit to assess patient and household symptoms and the socioeconomic impact of their test result and treatment access.

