### **3.2 END OF STUDY AND LENGTH OF STUDY**

The end of this study is defined as the date when 12 weeks of mobile testing and treating deployment has concluded or the end of “influenza season” as defined by the New Mexico Department of Health, whichever is last. As this is a single dose observational study, there are no follow-up visits scheduled as part of the study. All subjects receiving the therapeutic will receive a follow-up phone call 24-48 hours following administration of Xofluza. All enrolled subjects will receive a follow-up phone call 14-days following the initial screening visit to assess symptom resolution and socioeconomic impact of their test result. The end of the study is expected to occur 12 months after the last patient is enrolled to allow for complete data analysis and evaluation. In addition, the Investigator may decide to terminate the study at any time.

The total length of the study, from screening of the first patient to the end of the study, is expected to be approximately 15 months.

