The mobile testing unit will be deployed a minimum of 2 times per week following the determination of the influenza season by the New Mexico Department of Health. We expect to screen 50-100 patients per week for the duration of the influenza season (approximately 12 weeks) for a total of 600-1,2000 patients. With an anticipated 20-10% positivity rate for influenza, we expect at least 5-10 patients per week to be eligible for treatment for a total of 60-120 patients eligible over the course of the study. All subjects will be provided a survey to evaluated their ability to access respiratory virus testing and their acceptance of and trust in using a mobile unit for access to treatment and therapeutics. As per the New Mexico Test to Treat protocol, all patients will receive a follow-up phone call 24-48 hours following treatment. Additionally, all patients enrolled in the study will receive a follow-up phone call 14-days following the initial screening visit.

	Enrollment per deployment	Number of Deployments	Total Enrolled	Positivity Rate (Influenza)	Within Treatment Window	Expected Treated (total study)
Influenza Test to Treat	50-100	12	600-1200	10-20% (60-240)	90%	54-180

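### The AE reporting period closes on the day of an early study termination for anyone dosed in the previous 14 days, and Section 3.2 gives two incompatible ends of study that leave the cut-off open to a wider reading

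*Combined protocol and SAP*

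**What the plan says.** Section 5.3.1 opens the AE reporting period after consent and the start of treatment. The period "ends 14 days following the last administration of study treatment or study discontinuation/termination, whichever is earlier". The next sentence limits what follows: "After this period, investigators should only report SAEs that are attributed to prior study treatment". The section still carries an unresolved drafting instruction to adapt that sentence to the AESI section.

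Section 3.2 describes the end of study twice. The first statement is a definition: "The end of this study is defined as the date when 12 weeks of mobile testing and treating deployment has concluded", or the end of the influenza season "as defined by the New Mexico Department of Health, whichever is last". The second is an expectation: "The end of the study is expected to occur 12 months after the last patient is enrolled", to allow for data analysis. The total length, from first screening, "is expected to be approximately 15 months".

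Section 3.2 adds, as a separate matter, that the investigator may terminate the study at any time. Section 4.6.2, headed Study Discontinuation, repeats this and lists two possible reasons: adverse events that point to a health hazard, and unsatisfactory enrolment.

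On contact, Section 2.1 says: "Patients will receive a follow-up phone call 14-days following their initial screening visit". Sections 3.1, 3.2 and 6.1 promise the same call to all enrolled subjects, and treated patients are also called at 24 to 48 hours.

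**The concern.** The drug is given once, so a 14-day period is the whole planned safety observation for a treated patient. Taking the earlier of two dates shortens that period for patients dosed shortly before a termination. If the termination is for safety, these are the patients whose events are most needed for judging the hazard.

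Three kinds of information would fall outside the rule after the cut-off: non-serious AEs, SAEs judged unrelated to treatment, and deaths judged unrelated. Section 5.4.2.2 requires deaths to be reported regardless of attribution, but only within the same reporting period. Section 5.1.1.3 warns that serious bacterial infections may complicate influenza. An investigator could well judge such an event unrelated to the drug.

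The two ends of study add a second uncertainty. If planned completion were taken as a form of termination, and the first statement in Section 3.2 governed, the cut-off could also reach patients dosed late in the season when nothing has gone wrong.

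**Working it through.** **1. Which end of study fits the stated length?** Section 6.1 gives about 12 weeks of screening: 84 days / 30.4375 days per month = 2.76 months.
- First statement, with a season of about 12 weeks: 2.76 months. This does not give 15.
- Second statement: 2.76 + 12 = 14.76 months. This agrees with the stated 15 months after rounding.

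**2. Early termination (the narrow reading of the clause).** The inputs are the 54 to 180 expected treated patients in the Section 6.1 table, 84 days of deployment, and an assumed constant rate of treatment. The constant rate is suggested by the steady weekly screening figure in Section 6.1.
- Treated per day: 54/84 = 0.64 to 180/84 = 2.14.
- Patients still inside their 14 days when the study is stopped, at any time from day 14 to the last deployment: 14 × 0.64 = 9 to 14 × 2.14 = 30.
- A stop for poor enrolment would involve fewer. A stop 14 days or more after the last dose would involve none.

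**3. Planned end of study (only if termination is read to include it).** Let W be the weeks of deployment and g the days from the last deployment to the end of study. With uniform enrolment, the share of treated patients whose window is cut is max(0, 14 − g)/(7W).

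| Situation | Share cut |
|---|---|
| W = 12, g = 0 | 14/84 = 16.7% |
| W = 12, g = 3 | 11/84 = 13.1% |
| W = 12, g = 7 | 7/84 = 8.3% |
| W = 12, g ≥ 14 | 0% |
| Deployment runs to a season end at 16 weeks, g = 0 | 14/112 = 12.5% |
| Deployment runs to a season end at 20 weeks, g = 0 | 14/140 = 10% |
| 12-month date governs | 0% |

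Section 6.1 gives at least two deployments a week in the text (24 over 12 weeks) and 12 deployments in the table. The ceiling is the same for both: 4/24 = 2/12 = 1 in 6.

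In patients, the ceiling is 54/6 = 9 to 180/6 = 30. The upper figure of 180 does not follow from the table's own inputs, since 240 × 0.90 = 216. With 216 the ceiling is 36.

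**4. How much of the window is lost at that ceiling?**
- Continuous enrolment: a mean of 7 of 14 days among those affected, which is 1/6 × 7/14 = 8.3% of all AE follow-up time.
- Weekly deployments, study ending on the last deployment day: losses of 14 and 7 days, mean 10.5; 21/(14 × 12) = 12.5% of follow-up time.
- Twice-weekly deployments at 3- and 4-day spacing, same end: losses of 14, 11, 7 and 4 days, mean 9; 36/(14 × 24) = 10.7%.

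**The case against.** The strongest reply is that Section 5.3.1 does not speak of the end of study. It speaks of discontinuation or termination, and Sections 3.2 and 4.6.2 use those words for early stopping by the investigator. Section 3.2 sets the right to terminate beside its end-of-study statements as something additional. Nothing equates planned completion with termination. On that reading, neither statement in Section 3.2 triggers the cut-off. This stands, and it means that the late-season loss depends on a reading the documents do not favour. It does not answer the early-termination case, which arises on exactly that reading.

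A reader might infer that about one treated patient in six will lose follow-up. The documents do not support a fixed figure. The first end of study is the later of two dates, so it falls at the last deployment only if the season is over by then. The 15-month total supports the 12-month date, under which nobody is cut by planned completion.

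A reader might also infer that the 14-day hot-spot score windows would be incomplete. They would not be on account of this clause. Section 5.3.1 governs AE reporting only, and Section 2.1 plans the scores for 14 days after each intervention without reference to it.

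A claim that AE rates will be biased low also goes too far. Section 6.4 names a safety population of all dosed patients but specifies no rate. If a simple proportion were reported over that denominator, unreported late events would lower it, but this is conditional.

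The clause might be thought to close reporting for an individual who leaves the study early as well. The wording refers to the study, so that is uncertain, and Section 4.6.1 asks for every effort to obtain information on patients who withdraw.

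The safeguards are real but partial. Treatment-attributed SAEs stay reportable under Sections 5.3.1 and 5.4.2.10, and the calls are promised to all. However, the 14-day form in Appendix 1 covers household illness, symptom resolution and missed activities, and has no AE question. The call therefore does not replace the reporting rule.

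**Conclusion.** The point holds as a defect in the reporting rule and in the end-of-study wording. On the narrow reading of termination, an early stop during deployment ends routine AE reporting, and reporting of unattributed SAEs and deaths, for everyone dosed in the previous 14 days. At the planned constant rate this is about 9 to 30 patients. The effect arises only if the study is stopped early.

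Separately, the two ends of study in Section 3.2 are incompatible, and only the 12-month one fits the stated length. If termination were read to include the first, the share of treated patients affected would lie between 0% and 16.7%. The upper end needs 12 weeks of deployment, uniform enrolment and a study that ends on the last deployment day. If the study runs to its planned end and the 12-month date governs, the loss is zero.

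**What to change.** In Section 3.2, reconcile the two statements into one end-of-study definition that falls no earlier than the last participant's 14-day call. State the 12-month analysis period separately, as time for analysis.

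In Section 5.3.1, remove the alternative end at study discontinuation or termination, together with the rule that the earlier date applies. The protocol's own 14-day period then runs in full for every dosed patient, unless the patient dies or withdraws consent to contact. Resolve the leftover drafting instruction at the same time.

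The cost is an edit to two sections and, after an early stop, at most two more weeks of calls that are already planned. No dose, schedule or treatment rule changes.

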### **5.3.2        Assessment of Adverse Events**

All AEs and SAEs whether volunteered by the subject, discovered by study personnel during questioning, or detected through physical examination, laboratory test, or other means, will be reported appropriately. Each reported AE or SAE will be described by its duration (i.e., start and end dates), regulatory seriousness criteria if applicable, suspected relationship to Xofluza (see following guidance), and actions taken.

To ensure consistency of AE and SAE causality assessments, investigators should apply the following general guideline:

#### **Yes**

There is a plausible temporal relationship between the onset of the AE and administration of Xofluza, and the AE cannot be readily explained by the subject's clinical state, intercurrent illness, or concomitant therapies; and/or the AE follows a known pattern of response to Xofluza or with similar treatments; and/or the AE abates or resolves upon discontinuation of Xofluza or dose reduction and, if applicable, reappears upon re-challenge.

#### **No**

Evidence exists that the AE has an etiology other than Xofluza (e.g., preexisting medical condition, underlying disease, intercurrent illness, or concomitant medication); and/or the AE has no plausible temporal relationship to Xofluza administration (e.g., cancer diagnosed 2 days after first dose of Xofluza).

Expected adverse events are those adverse events that are listed or characterized in the Package Insert (P.I.).

Unexpected AEs are those not listed in the PI or current IB or not identified. This includes AEs for which the specificity or severity is not consistent with the description in the PI or IB. For example, under this definition, hepatic necrosis would be unexpected if the PI or IB only referred to elevated hepatic enzymes or hepatitis.

## **5.4 PROCEDURES FOR ELICITING, RECORDING, AND REPORTING ADVERSE EVENTS**

### **5.4.1 Eliciting Adverse Events**

A consistent methodology for eliciting AEs at all subject evaluation time points should be adopted. Examples of non-directive questions include:

- "How have you felt since your last clinic visit?"
- "Have you had any new or changed health problems since you were last here?"

### **5.4.2 Specific Instructions for Recording Adverse Events**

Investigators should use correct medical terminology/concepts when reporting AEs or SAEs. Avoid colloquialisms and abbreviations.

#### **5.4.2.1 Diagnosis vs. Signs and Symptoms**

If known at the time of reporting, a diagnosis should be reported rather than individual signs and symptoms (e.g., record only liver failure or hepatitis rather than jaundice, asterixis, and elevated transaminases). However, if a constellation of signs and/or symptoms cannot be medically characterized as a single diagnosis or syndrome at the time of reporting, it is acceptable to report the information that is currently available. If a diagnosis is subsequently established, it should be reported as follow-up information.

#### **5.4.2.2 Deaths**

All deaths that occur during the protocol-specified AE reporting period (see Section **Error! Reference source not found.**), regardless of attribution, will be reported to the appropriate parties. When recording a death, the event or condition that caused or contributed to the fatal outcome should be reported as the single medical concept. If the cause of death is unknown and cannot be ascertained at the time of reporting, report "Unexplained Death."

#### **5.4.2.3 Preexisting Medical Conditions**

A preexisting medical condition is one that is present at the start of the study. Such conditions should be reported as medical and surgical history. A preexisting medical condition should be re-assessed throughout the trial and reported as an AE or SAE only if the frequency, severity, or character of the condition worsens during the study. When reporting such events, it is important to convey the concept that the preexisting condition has changed by including applicable descriptors (e.g., "more frequent headaches").

#### **5.4.2.4 Hospitalizations for Medical or Surgical Procedures**

Any AE that results in hospitalization or prolonged hospitalization should be documented and reported as an SAE. If a subject is hospitalized to undergo a medical or surgical procedure as a result of an AE, the event responsible for the procedure, not the procedure itself, should be reported as the SAE. For example, if a subject is hospitalized to undergo coronary bypass surgery, record the heart condition that necessitated the bypass as the SAE.

Hospitalizations for the following reasons do not require reporting:

- Hospitalization or prolonged hospitalization for diagnostic or elective surgical procedures for preexisting conditions
- Hospitalization or prolonged hospitalization required to allow efficacy measurement for the study, or
- Hospitalization or prolonged hospitalization for scheduled therapy of the target disease of the study

#### **5.4.2.5 Assessment of Severity of Adverse Events**

The AE severity grading scale for the NCI CTCAE (v5.0) will be used for assessing AE severity. Table below should be used for assessing severity for AES that are not specifically listed in the NCI CTCAE.

**Table 1 Adverse Event Severity Grading Scale for Events Not Specifically Listed in NCI CTCAE Grade Severity**

Grade	Severity
1	Mild; asymptomatic or mild symptoms; clinical or diagnostic observations only; or intervention not indicated
2	Moderate; minimal, local, or non-invasive intervention indicated; or limiting age-appropriate instrumental activities of daily living a
3	Severe or medically significant, but not immediately life-threatening; hospitalization or prolongation of hospitalization indicated; disabling; or limiting self-care activities of daily living b,c
4	Life-threatening consequences or urgent intervention indicated d
5	Death related to adverse event d

NCI CTCAE = National Cancer Institute Common Terminology Criteria for Adverse Events.

Note: Based on the most recent version of NCI CTCAE (v5.0), which can be found at:

[http://ctep.cancer.gov/protocolDevelopment/electronic\\_applications/ctc.htm](http://ctep.cancer.gov/protocolDevelopment/electronic_applications/ctc.htm)

- a. Instrumental activities of daily living refer to preparing meals, shopping for groceries or clothes, using the telephone, managing money, etc.
- b. Examples of self-care activities of daily living include bathing, dressing and undressing, feeding oneself, using the toilet, and taking medications, as performed by patients who are not bedridden
- c. If an event is assessed as a "significant medical event," it must be reported as a serious adverse event
- d. Grade 4 and 5 events must be reported as serious adverse events

